In this study we aim at comparing using synthetic absorbable monofilament sutures in uterine closure during caesarean delivery with using synthetic absorbable multifilament sutures as regards the reduction in the rate of isthmocele.

1. INTRODUCTION/ REVIEW

Cesarean section is the most common type of obstetric surgery (**Mistry k et al.,2013**) with substantial increases in the number of Cesarean section deliveries in middle- and high-income countries in recent years. (**Betrán AP et al.,2014**). The rates of caesarean section vary by region, accounting for 3.3% of deliveries in Africa, 33.7% in Latin America, 27.3% In Asia, and 40.5% in China, with a global average of 15.9% (**WHO,2009**). However, there are short and long-term complications of Cesarean section, including effects on other surgical procedures, as well as on subsequent Cesarean section operations. One of the most common complications is the isthmocele, which is noted more frequently with increasing Cesarean section operations. (**Villar J et al.,2007**).

Isthmocele can develop after transverse incision of the lower uterine segment. This pouch-like structure, first described by Morris in 1995, also called isthmocele, niche, or caesarean scar dehiscence, is located at the site of the old caesarean scar on the anterior uterine isthmus. (**Baranov A et al.,2016**).

Sutures are an essential part of any major surgery, serving to hold opposing tissues together and accelerate the healing process, resulting in decreased scarring of the affected areas.

Many authors have investigated possible risk factors related to isthmocele, particularly those

related to uterine closure, number of caesarean births, uterine position, and labour before caesarean delivery. (**Tower AM1 et al., 2013**). However, studies examining the role of the suture material in formation of isthmocele are limited.

Isthmocele has been implicated as an etiologic factor in clinical problems, such as rupture of the uterus during a subsequent pregnancy, ectopic pregnancy at the caesarean scar, caesarean scar endometriosis, secondary infertility, postmenstrual spotting and dysmenorrhea. . (**Bij de Vaate AJ, 2011**).

The development of isthmocele is associated with a deficiency of uterine scar healing. The prevention of isthmocele should be the first and most essential aim of overcoming isthmocele-related complications. Therefore, numerous studies have recently focused on the development and prevention of isthmocele. (**McCurdy R et al.,2017**).

To assess the healing of scar and the risk of uterine rupture and other complications, ultrasonography is used in the evaluation of uterine scar 6 weeks after delivery. It has generally been found that, the thicker the uterine scar, the lower the rate of complications. This may be due to that the thicker scar is stronger, and thus performs better than a thinner one. (**Litzka, 2021**).

Closure of the uterine incision is a key step in caesarean delivery, correct approximation of the cut margins is of a critical value. (**Vikhareva Osser , 2011**). Limited data are available to evaluate the role of the suture materials in uterine scar healing and the development of isthmocele. (**Başbuğ A et al.,2019**).

Monofilament suture (polyglycolide-co-caprolactone) material is made of a single strand, which is relatively more resistant to harboring microorganisms. It also exhibits less resistance to passage through tissue unlike multifilament suture which inflict more microtrauma as they pass through tissues. However, great care must be taken in handling and tying a monofilament suture, because crushing or crimping of the suture can weaken it and lead to undesirable and premature suture failure. Multifilament suture material (polyglactin) is composed of several filaments twisted or braided together. It generally has greater tensile strength and better pliability and flexibility than monofilament suture material, and it handles and ties well. Multifilament sutures also induce a more intense inflammatory response and contribute to larger knot volumes than monofilaments. However, because multifilament materials have increased capillarity, the increased absorption of fluid may facilitate the introduction of pathogens, which increases the risk for wound infection and dehiscence. (**Islam A, et al.2011**)

An internationally recognized definition for isthmocele was only agreed upon in 2019 by the European task force, which defined a cesarean scar defect as an “indentation at the site in the cesarean section scar with a depth of at least 2 mm.” This definition was further subclassified as follows: simple niche, simple niche with one branch, and complex niche (with more than one branch). A branch was defined as the thinner part of the main niche that is directed toward the serosa and has a width smaller than the main niche. Residual myometrial thickness "RMT" is the distance between the tip of the hypo echoic triangle and the surface of anterior uterine wall measured by mm.) At the apex of the main niche, the RMT is often decreased. (**Jordans IPM et al,2019**).

The present study aimed to evaluate how the use of Monocryl (monofilament synthetic

absorbable sutures) instead of Vicryl (multifilament synthetic absorbable sutures) in the continuous double-layer unlocked closure technique for low transverse uterine incisions impacts uterine scar healing after Cesarean section.

2.AIM / OBJECTIVES

To evaluate the impact of using synthetic absorbable monofilament sutures in uterine closure during caesarean delivery compared to using synthetic absorbable multifilament sutures on the development of Isthmocele.

Research Question:

Will uterine closure using synthetic absorbable monofilament sutures during caesarean delivery reduce the incidence of isthmocele compared to uterine closure using synthetic absorbable multifilament sutures?

3.METHODOLOGY:

Patients and Methods/ Subjects and Methods/ Material and Methods

- **Study Type:** A Randomized Controlled Trial.
- **Study Setting:** The study will be conducted at Ain Shams University Maternity Hospital (labour ward and the Ultrasound (Special Care unit for the fetus).
- **Study Period:** 1 year. (from December 2023 to December 2024)
- **Sampling Method:** Convenience sample from El-Demrdash hospital population that attending the ER.
- **Study Population:** The study will be conducted on (140) women divided into two equal groups.
- **Sample Justification:** Based on the results of **Saccone et al. (2022)**, with the mean defect width in mm in monofilament group 2.9 ± 0.6 and in multifilament group 3.4 ± 1 mm, alpha error 5% and power of study 80%, the required sample is 140 patients 70 in each group. The program for sample size calculation is STATA 10.

Inclusion criteria:

- Age: 20-45 years old
- Singleton pregnancy.
- Gestational age between 37 completed weeks to 42 weeks.
- Patients undergoing elective primary caesarean section

Exclusion criteria:

- History of uterine surgery (e.g. hysterotomy, myomectomy, perforation, caesarean section). (to be able to differentiate between the recent CS scar and the old scar)
- Abnormal placental invasion (placenta previa and accrete) (more liable to undergo Cesarean hysterectomy)
- Uterine anomalies (e.g., septum, Mullerian anomalies or fibroids). (may be localized at the suture line and therefore affect the scar)

- Drugs intake that affects bleeding or tissue healing e.g., anti-coagulants, immunosuppressive drugs and chronic use of steroids (more than 14 days pre-operative)
- Any medical Co-morbidity (diabetes mellitus, Hypertension and Thyroid abnormalities) (more liable to affect the healing)

● **Randomization:**

Randomization will be done using computer generated random sequence. Study population will be randomized into one of the two groups:

- Group (I): 70 patients will undergo uterine closure using Monofilament suture material. (A) (1/0, Monocryl®).
- Group (II): 70 patients will undergo uterine closure using Multifilament suture material. (B) (1/0, Vicryl®).

● **Allocation concealment:**

One hundred and forty opaque envelopes will be numbered serially and each envelope with the corresponding number which denotes the allocated group will be put according to randomization table. Then all envelopes will be closed and put in one box. When the first patient is included, the first envelope will be opened and the patient will be allocated according to the letter inside.

● **Blinding:**

Double blinding is difficult because the surgeon will perform the procedure. However, the measured outcomes are objective and unlikely to be biased by lack of blinding. Patient is blinded, sonography (measuring the outcome is blind to type of repair). Statistical analysis will be blinded to group allocation (single blinded)

● **Study procedures and interventions:**

The patients will be randomly divided into 2 groups using a computer-generated number based on the type of suture materials to be used for the continuous double-layer unlocked closure of the low transverse uterine incision during Cesarean section.

Surgery will be done by the most senior resident.

Baseline Evaluation

All participants will be submitted to:

- Complete history taking including personal history, history of present pregnancy, past history, menstrual history, obstetric history, medical history and family history.
- General, abdominal, and pelvic examination.
- Laboratory investigation: complete blood picture, coagulation profile, random blood sugar, liver enzymes and serum creatinine.
- Ultrasound examination: Basic ultrasound examination will be done for all women to assess (fetal life, Biometry, amniotic fluid and placental location).

Preoperative antibiotic prophylaxis:

Two grams of cefazolin (under trade name of **Zinol®** manufactured by Pharco B International, New Borg El Arab, Egypt.) to be administered 15 – 60 minutes before incision. (**Bratzler et al., 2013, Witt et al, 2013**).

Anesthesia: All anesthesia techniques can be considered.

Operative steps: “All surgeries will be performed by the same surgeon rank”.

- Antisepsis of urethral meatus and catheterization under aseptic conditions.
- Vaginal toilet will be done to all patients with povidone iodine solution before the operation.
- Scrubbing the abdomen will be done by using povidone iodine solution 10%.
- All women will undergo Pfannenstiel-Kerr cesarean section.
- Open of the anterior abdominal wall in layers by scalpel.
- Lower segment uterine incision.
- Deliver of the head by firm wrist flexion, then insertion of fingertips into the uterine incision and advance them around the fetal head to deliver the shoulder and the body
- Deliver the placenta by controlled cord traction.
- Oxytocin (5 IU by slow intravenous injection) will be used to encourage contraction of the uterus and to decrease blood loss.
- After delivery of the fetus and placenta:

Group (A): "Interventional group"

Closure of the uterus in two layers in continuous unlocked sutures using synthetic absorbable monofilament suture (Monocryl 1). (EGYMONOCRYL® manufactured by Taisier-Med Obour, Egypt).

Group (B): "Control Group"

Closure of the uterus in two layers in continuous unlocked sutures using synthetic absorbable multifilament suture (Vicryl 1) (EGYSORB® manufactured by Taisier-Med Obour, Egypt).

- Fascia will be closed as continuous running sutures using an absorbable suture (Vicryl 1)
- Subcutaneous closure: The subcutaneous adipose layer should be closed when the layer is \geq 2 cm by Vicryl 0. (**Chelmow et al., 2004**).
- Skin closure: Reapproximation of the skin will be performed with subcuticular suture using 2-0 polypropylene nonabsorbable suture (EGYPROLENE® manufactured by Taisier-Med Obour city, Cairo, Egypt.).

Post-operative care:

- All patients will receive Non-Steroidal Anti-Inflammatory drugs immediately postoperative then one ampoule 12 hours postoperative, (**Altman, 2015**). and according to Ain Shams Maternity hospital protocol.
- Vital signs (pulse, blood pressure, temperature) of the patients will be measured four times daily during hospitalization.
- At 6 h postoperatively, urinary Foley catheters will be removed and oral intake with clear fluids will be started. (**ACOG, 2008**).
- A venous blood sample for complete blood count examination will be withdrawn after 24 hours postoperative.
- Regular antipyretic will not be used so as not to mask possible postpartum pyrexia.

- Patients will be instructed for postoperative wound care e.g.: to always keep wound dressing dry and clean and in case it gets wet it is to be dressed in an aseptic non-touch technique.
- Follow up for assessment after 1 week of delivery to check the wound, and after 6 months to undergo the Ultrasound.

Outcomes:

Primary outcome: the incidence of isthmocele by transvaginal ultrasound 6 months after delivery.

Isthmocele is defined as an anechoic defect communicating with the endometrial cavity at the anterior wall of the lower uterine segment.

For each case the following isthmocele measurements will be obtained:

1. The thinning extent, calculated by a ratio between (a) and (b).
 - (a): thickness of the residual myometrium over the defect.
 - (b): total intact myometrium. A severe deficiency occurs when more than 50% of myometrium is lost at the niche scar site.
2. Width of isthmocele (c)
3. Depth of isthmocele (d)

Furthermore, we will record the shape of the defect (i.e., triangular, round, or oval). Moreover, the residual myometrial thickness will be measured. In case of isthmocele, RMT overlying the defect and the adjacent myometrial thickness fundal to the defect will be recorded. According to previous literature, the diagnosis of isthmocele was made in case of depth of the defect at least 2.00 mm in the longitudinal plan. (**Naji O et al, 2012**).

[figure not shown]

Figure 1.

Secondary outcomes:

1. Amount of blood loss.

ABL = weight kg * age sex factor (65ml/ kg)*initial HGB(g/dl)-final HGB(g/dl) / 12-hours postoperative"./ intial HGB (g/dl) (M. E. Brecher,2003)

2. Need for extra hemostatic sutures.
3. Need for blood transfusion.

4. Wound infection.
5. Hospital stay after the delivery.
6. Post-operative fever.

(Defined as a temperature higher than 38 c on two consecutive postoperative days or higher than 39 c on any postoperative day). **(Abdelmaseeh TA et al, 2022)**

7. Primary Postpartum hemorrhage. (Defined as Cumulative blood loss greater than 1000 mL with signs and symptoms of hypovolemia within 24 hours of the delivery). **(ASOG,2017)**.

- **Statistical analysis:**

Based on the results of Saccone et al 2022 , with the mean defect width in mm in monofilament group 2.9 ± 0.6 and in multifilament group 3.4 ± 1 mm, alpha error 5% and power of study 80%, the required sample is 140 patients 70 in each group . The program for sample size calculation is STATA 10.

- **Ethical Consideration:**

This study will be done after approval of the ethical committee of the department of obstetrics and gynecology, faculty of medicine, Ain Shams University. Informed consent will be taken from all participants before recruitment in the study, and after explaining the purpose and procedures of the study. The investigator will obtain the written, signed informed consent of each subject prior to performing any study specific procedures on the subject. The investigator will retain the original signed informed consent form. All laboratory specimens, evaluation forms, reports, and other records that leave the site will not include unique personal data to maintain subject confidentiality. The study will be based on the investigator self-funding.

Protocol approval:

Before the beginning of the study and in accordance with the local regulation followed, the protocol and all the corresponding documents will be declared for ethical and research approval by the council of OB/GYN Department, Ain Shams University according to the the ethical committee

Patient right to withdraw

4. REFERENCES:

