Chorioamnionitis in that pregnancy	
Medical history	
Surgical history	
Pre-operative haemoglobin level	
Post-operative haemoglobin level	
Total blood loss	
Number of received blood components	
Procedure time	

ICU admission	
Hospital stay	
Post-operative fever	
Wound infection	
Trans vaginal US after 6 months → Isthmocele? Yes or NO if Yes → Isthmocele measurements will be obtained.	
Bladder injury in that Cesarean section	
Post-partum hemorrhage

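### The stated width inputs give 43–44 measured widths per group at 80% power, not 70, and the protocol states no step that leads from one to the other

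*Protocol*

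**What the plan says.** The Sample Justification item in section 3 (Methodology) takes from a cited trial a "mean defect width in mm in monofilament group 2.9 ± 0.6 and in multifilament group 3.4 ± 1 mm" and goes on: "alpha error 5% and power of study 80%, the required sample is 140 patients 70 in each group". It names the software (STATA 10) but gives no test, sidedness or command. The Statistical analysis paragraph repeats the same means, spreads, error rates and total.

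Two other places bear on what is being counted. The case record form has an entry for isthmocele at the 6-month scan and adds: "if Yes → Isthmocele measurements will be obtained". The Outcomes section introduces the same measurements with "For each case the following isthmocele measurements will be obtained", which does not say clearly whether a case is any woman scanned or a woman with a defect. The primary outcome is not width but "the incidence of isthmocele by transvaginal ultrasound 6 months after delivery".

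**The concern.** This is the only sample size justification in the protocol, and it gives what a two-means calculation needs: two means, two spreads, alpha, power and equal allocation. Only the sidedness and the test are left open. A reader should therefore be able to recover 70 per group to within rounding. The recovered figure is well below 70, so at least one of the following must be true: a different standard deviation was used, a different power was used, an allowance was added without being reported, or the calculation is wrong. The text does not show which.

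What is at stake is whether the quoted 80% can be relied on. It is not the power for width with 70 measured widths per group. With 70 women randomised per group it would be the power only if the numbers of measured widths happened to produce it, and the protocol gives no expected number.

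**Working it through.** **Inputs** (Sample Justification, repeated under Statistical analysis): means 2.9 and 3.4 mm, difference 0.5 mm; standard deviations 0.6 and 1.0 mm (reading ± as SD); alpha 5%; power 80%; 1:1 allocation. Sidedness is not stated, so both cases are shown.

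**Step 1. Attempt to reproduce 70 per group.** With the normal formula for two means with unequal SDs,

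n per group = (z for alpha + z for power)² × (SD₁² + SD₂²) / difference²

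- Two-sided 5%: (1.96 + 0.8416)² × (0.36 + 1.00) / 0.25 = 7.849 × 5.44 = 42.7, so **43**.
- Welch t-test, two-sided: 43 per group gives power 0.792 and 44 gives 0.801, so **44**.
- One-sided 5%: (1.645 + 0.8416)² × 5.44 = 33.6, so 34; by Welch, 35 (power 0.805).

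None of these is near 70, and the one-sided reading is further away.

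**Step 2. Power at 70 measured widths per group.** The standard error is √(1.36/70) = 0.139 and 0.5/0.139 = 3.59. Normal power is Φ(3.59 − 1.96) = 0.948; Welch power is 0.945. The protocol states 0.80.

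**Step 3. What would lead to 70?**

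| Route | Result per group | Position in the protocol |
|---|---|---|
| SD 1.0 in both groups, then 10% loss | 7.849 × 2/0.25 = 62.8, so 63; 63/0.9 = 70 | Neither the common SD nor the loss is stated; the quoted monofilament SD is 0.6 |
| Stated SDs, 95% power | (1.96 + 1.645)² × 5.44 = 70.7, so 71 (Welch 72) | Stated power is 80% |
| Stated SDs, 80% power, some women without a width | 43/70 = 61% or 44/70 = 63% must contribute a width | No isthmocele rate or loss is stated |

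Each route needs an input that is absent from the protocol or differs from what it states.

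**Step 4. Power for width if fewer than 70 per group contribute one.** The protocol gives no expected number, so these counts are assumptions chosen only to show the range. Two-sided Welch test, stated SDs, equal numbers in both groups:

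| Widths per group | Share of 70 | Power |
|---|---|---|
| 21 | 30% | 0.479 |
| 28 | 40% | 0.602 |
| 35 | 50% | 0.703 |
| 44 | 63% | 0.801 |
| 70 | 100% | 0.945 |

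Because the SDs differ, the split matters as well as the total. Of 83 widths, 30 monofilament and 53 multifilament give 0.803, while 53 and 30 give 0.683. An expected number is therefore needed for each group, not only in total.

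**The case against.** The strongest reply is that two different units are being compared. The formula returns measured widths, while the protocol's 70 are women randomised. If about 37% of women had no width, through absence of a defect or loss before the 6-month scan, 70 women would yield 44 widths and the 80% would be right. Alternatively, the larger SD may have been applied to both groups as a cautious choice and 10% added for loss, which gives exactly 70 by the normal formula (a t-test would need 64, and 64/0.9 = 71.1). On either account the fault is incomplete reporting rather than a wrong number. On width alone the discrepancy also errs towards more women than the formula needs, and width is not the primary outcome.

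Part of this stands. The document cannot distinguish miscalculation from an unreported step, and the result must not be read as showing that the trial is over-sized. Using the larger SD throughout would be a defensible choice had it been declared. But the paragraph presents 70 as what its listed inputs require, and they do not require it. The discrepancy is also not reliably conservative: under the case record form's wording, the number of widths could fall below 44 per group, and power for width would then be below 80%.

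**Conclusion.** The concern holds. From its own inputs the calculation gives 43–44 measured widths per group two-sided (34–35 one-sided) against a stated 70, and about 94–95% power at 70 widths per group against a stated 80%. This rests on reading the ± values as standard deviations, which is the natural reading in a comparison of means. The choice between the normal formula and the t-test changes the answer by only one per group.

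The power for width that 70 randomised women per group will actually give cannot be determined from the protocol, because the number contributing a width is not stated. None of these figures says anything about the power for isthmocele incidence.

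**What to change.** Correct the paragraph under Sample Justification and its repeat under Statistical analysis, leaving enrolment at 140:

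1. State that the quoted means and SDs, at two-sided 5% and 80% power, need 43–44 measured widths per group, and name the test.
2. Then do one of two things. Either give the SD, power and allowance that were actually used to reach 70, or restate the power for width at the number of widths expected in each group, with that assumption shown. About 94–95% may be quoted only if all 70 women per group are expected to contribute a width.
3. Do not present the width figure as power for the primary outcome.

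The cost is the wording of one paragraph in two places. Enrolment, procedures and data collected stay as they are.

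### The allocation envelope is opened at inclusion, before the step at which the arms first differ, so the arm may be known while eligibility can still change

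*Protocol*

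**What the plan says.** All places are in the protocol.

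- **Section 3, Allocation concealment.** There are 140 opaque, serially numbered, closed envelopes. The opening rule is: "When the first patient is included, the first envelope will be opened and the patient will be allocated according to the letter inside". It is worded for the first woman and evidently meant for each one after her.
- **Ethical Consideration.** "Informed consent will be taken from all participants before recruitment in the study". This points to inclusion before surgery, although no clock time is given.
- **Section 3, Operative steps.** Preparation, incision, delivery of the baby and placenta, and oxytocin are described once for all women. The text divides into two groups only under "After delivery of the fetus and placenta", where the uterus is closed with one suture or the other.
- **Section 3, Exclusion criteria.** These include "Abnormal placental invasion (placenta previa and accrete" and "Uterine anomalies (e.g., septum, Mullerian anomalies or fibroids". The reason given for the second is that such lesions may lie at the suture line.
- **Section 3, Baseline Evaluation.** The listed ultrasound covers fetal viability, fetal measurements, fluid and where the placenta lies. It mentions neither fibroids nor uterine anomalies.
- **Section 3, Blinding.** "Double blinding is difficult because the surgeon will perform the procedure". The sonographer is masked: "Patient is blinded, sonography (measuring the outcome is blind to type of repair".

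The protocol does not say who opens the envelope, when the surgeon is told, or what happens to a woman found ineligible after her envelope is opened.

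**The concern.** Sealed envelopes protect eligibility decisions only while they are sealed. Here they are opened at inclusion, and two kinds of event can follow before the uterus is closed.

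First, eligibility can change. Fibroids, an anomaly or an adherent placenta may first be seen at operation, and a planned case may be cancelled. A decision to keep or drop the woman could then be made by someone who knows her arm. A masked sonographer six months later cannot correct for who was left out.

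Second, the arm may be known during steps that do not depend on it. The uterine incision makes the scar that the primary outcome examines. Blood loss, a secondary outcome, is calculated from the haemoglobin change across the operation and so includes bleeding before closure.

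Both exposures can largely be avoided, because the allocation is not needed until closure.

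**Working it through.** The point is procedural, so the main check sets the passages against each other in time. A short calculation then tests whether lost numbers matter.

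**1. Order of events**

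- Consent, then recruitment (Ethical Consideration).
- Envelope opened at inclusion (Allocation concealment).
- Common operative steps up to delivery of the placenta (Operative steps).
- First step that differs by arm: uterine closure (Operative steps).

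No passage delays the opening to theatre or to closure. The letter is therefore revealed before it is needed. The length of the gap cannot be stated, because inclusion is not placed in time relative to surgery.

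**2. Which exclusions can surface in the gap**

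- Previous uterine surgery, drug use and comorbidity: found by history, so unlikely to surface late.
- Placenta previa: position is on the ultrasound list. Depth of invasion is not.
- Fibroids and uterine anomalies: not on the ultrasound list, and visible to the surgeon.

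The gap is therefore mainly fibroids, anomalies, unrecognised invasion and cancellations.

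**3. Spare allocations**

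140 envelopes − 140 women = 0 spare.

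**4. Does the loss of numbers matter?**

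Inputs from Sample Justification: mean defect width 2.9 (SD 0.6) against 3.4 (SD 1) mm, so δ = 0.5 and s₁² + s₂² = 0.36 + 1 = 1.36; alpha 5%, taken as two-sided because the sidedness is not stated; power 80%; 70 per group.

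The plan's own figure first: n per group = (1.960 + 0.842)² × 1.36 / 0.25 ≈ 7.85 × 5.44 ≈ 42.7, so 43. The stated 70 is not reproduced at 80% power. That is a separate matter and does not bear on this point.

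Power with n per group = Φ(0.5 / √(1.36/n) − 1.96). At n = 70: Φ(3.587 − 1.960) = Φ(1.627) = 94.8%. As a harder case, SD 1 in both arms replaces 1.36 by 2 and gives 84.1%.

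The loss rates below are assumptions; the documents give none.

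| Assumed loss | Envelopes of 140 | Left per group | Power, SD 0.6 and 1 | Power, SD 1 in both |
|---|---|---|---|---|
| 0% | 0 | 70 | 94.8% | 84.1% |
| 1% | 1.4 | 69.3 | 94.6% | 83.7% |
| 2% | 2.8 | 68.6 | 94.4% | 83.4% |
| 5% | 7 | 66.5 | 93.8% | 82.2% |
| 10% | 14 | 63.0 | 92.6% | 80.1% |

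These figures concern defect width, not the primary outcome, which is isthmocele incidence. The protocol gives no incidence rates, so power for the primary outcome cannot be checked. Purely as an assumed range, take control rates of 20% to 60%, reduced to 0.5 or 0.67 of that value. A 5% loss then lowers power by 0.7 to 2.3 percentage points; for example, 40% against 20% goes from 73.8% to 71.6%.

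The cost in numbers is small on every set of inputs tried. What remains is the risk of bias.

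**The case against.** Several parts of the case against this point stand.

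- **A reader might infer that the surgeon knows the arm throughout the operation.** The protocol does not say so. It names neither the person who opens the envelope nor the moment the surgeon is told. It supports only that the arm may be known early.
- **A reader might infer that women found ineligible at operation will be dropped.** No passage says this. Their handling is commonly left to a SAP, which was not available here, so silence on the analysis set is not a fault by itself. The opening rule is different: the protocol states it, and states it at a time that creates the problem.
- **Concealment before enrolment is intact.** Opening a sealed, numbered envelope only after inclusion prevents foreknowledge at recruitment. The weakness arises after allocation, and analysing everyone as allocated would answer much of it even if the timing stayed as it is. It would not address knowledge of the arm before closure, and a woman with no study closure would still have used an allocation.
- **A reader might count a change from elective to urgent surgery as a wasted envelope.** That is too strong. Such a change is not among the listed exclusions, and the woman still has a uterine closure.
- **Later opening masks little.** The surgeon must know the suture from closure onward, so extra haemostatic sutures and later blood loss stay unmasked. The steps before closure are the same in both arms, and influence on them is possible but not shown. The primary outcome is read by a masked sonographer, which limits assessment bias.

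None of this supplies a reason to reveal the allocation before closure.

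**Conclusion.** The point holds as a modest, cheap improvement. The protocol reveals the allocation at inclusion, the arms first differ at uterine closure, and some listed exclusions can first appear between the two. There are no spare envelopes and no rule for such women.

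The size of any bias cannot be given. It depends on how often eligibility changes after opening and on whether the people deciding know the arm, and the documents give neither. The effect on power is small under assumed losses of up to 10%: on the width inputs it stays at or above 92.6%, or 80.1% with the larger SD in both arms. Lost numbers are therefore not the argument.

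The conclusion assumes that inclusion precedes surgery, as consent before recruitment suggests, and that no other document moves the opening to theatre.

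**What to change.** Replace the opening sentence under Allocation concealment with a rule to this effect: existing theatre staff open the next numbered envelope after the placenta is delivered, once eligibility at operation is confirmed and immediately before uterine closure. A woman found ineligible, or whose case is cancelled, before that moment uses no envelope, and the next number passes to the next eligible woman. Add that every woman whose envelope was opened is analysed in her allocated arm. Consent stays where it is, before surgery.

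The cost is a small protocol change, both sutures ready in theatre, and a member of the theatre team to open the envelope during the case. Because the protocol allows any form of anaesthesia, some women may be awake, so the letter should not be read aloud if the patient is to stay masked. The change does not mask the closure itself or anything after it.
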